8.5 Analyses of the Key Secondary Outcome Measures

The key secondary outcome, days to first injection, will be summarized by induction procedure. It will be compared between the two induction procedures in the inducted population using a Cox proportional hazards model. The log hazard rate of receiving the first XR-NTX injection will be modeled as a function of induction procedure (RP vs SP), step and site. The SAS PHREG procedure will be used to estimate the hazard ratio for the induction procedures. The 95% Wald Confidence limits will be estimated.

SAS Code example:

```
proc phreg data=inject;
  class trt step site;
  model time*censor (0) = trt step site;
  hazardratio trt;
run;
```

where:

- time - is the time to event variable, i.e., the days to first injection.
- censor - is the censoring indicator variable. The censoring value (censor=0) means censored. However, given the analysis is conducted in the inducted population only, there will be no censored observations, i.e., censor=1 for all observations.
- trt - is the variable that defines the induction procedure (RP or SP)

- step - is 1 through 5
- site - is the site code for the 6 sites.

The other key secondary outcomes including craving for opioids (VAS) and opioid withdrawal measures (COW and SOW) will be summarized in tabular and graphical form for each day of the induction phase by induction procedure. In the Standard Procedure, scores will be summarized by Buprenorphine Day, Buprenorphine Washout Day, Naltrexone Day, Day of XR-NTX Injection Success or Day of XR-NTX Injection Failure. In the Rapid Procedure, scores will be summarized by Pre-Buprenorphine Day, Buprenorphine Day, Buprenorphine Washout Day, Naltrexone Day, Day of XR-NTX Injection Success or Day of XR-NTX Injection Failure.

Longitudinal opioid craving and withdrawal scores may be analyzed using mixed-effects models adjusting for induction procedure, site, step, and days since admission. The presence of at least one moderate to severe daily COWS score (maximum score ≥ 12) and presence of moderate to severe average daily COWS score (average score ≥ 12) will be analyzed using a mixed-effects model with logit-link function.

SAS code example that may be used to analyze binary COWS outcome:

```
proc glimmix data = secondout method = quad IC=PQ;  
  class patid site trt(ref='SP') step (ref='1');  
  model outcome (event='1')= trt site day step/ dist = binary link = logit solution oddsratio;  
  random intercept / subject=patid type=ar(1);  
run;
```

where:

- trt - is the variable that defines the induction procedure (RP or SP)
- outcome - is the presence of moderate to severe daily COW score (Yes=1 or No=0)
- step - is 1 through 5
- site - is the site code for the 6 sites.
- day- days since admission to the unit
- patid- participant ID

SAS code example that may be used to analyze continuous SOWS and VAS outcomes:

```
proc mixed data = secondout;  
  class patid site day_cat trt(ref='SP') step (ref='1');  
  model outcome = trt site day step/ solution cl;  
  random intercept / subject = patid;  
  repeated day_cat/ type = AR(1) subject = patid;  
  estimate "trt effect" trt 1 -1;  
run;
```

where:

- trt - is the variable that defines the induction procedure (RP or SP)
- outcome - is either mean SOWS or mean VAS score
- step - is 1 through 5
- site - is the site code for the 6 sites
- day - days since admission to the unit (continuous)
- day_cat- days since admission to the unit (categorical) as required by the repeated statement in the model
- patid- participant ID

Retention in the trial to receive at least one XR-NTX injection after the first inpatient injection as captured on the XR-NTX Administration (INN) form will be analyzed similarly to the primary outcome using a mixed-effects model with logit-link function.

Frequency of targeted safety events, overdose episodes and SAEs by relationship to study medication will be reported. Safety data analysis is provided in detail in Section 9.0.

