11.0 SIGNIFICANCE TESTING AND MULTIPLICITY

There is only one primary outcome and therefore no adjustments for multiple testing are planned for the primary outcome analysis. The primary outcome and the supportive analysis for the primary outcome will use a one-sided test with 2.5% type I error rate. A similar error rate will be used if the test of superiority is performed. A restricted list of secondary outcomes was chosen a priori, and, in addition, the key secondary outcomes are not intended to be confirmatory in nature. Therefore, no multiple adjustments are planned for analyzing multiple secondary outcome measures. When multiple tests are conducted, the chance of finding a significant difference in one of the tests, when in fact no difference exists, is greater than the stated type I error rate. The investigators are aware of the issues associated with multiple testing and will interpret results with caution. The secondary outcomes will use a two-sided test with 5% type I error rate.

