³ Visual Analog Scale for question "Think about your craving for opioids. How intense is it right now?"

⁴ Visual Analog Scale for question "Think about your desire to use opioids in the past 24 hours. How intense was your strongest desire to use?"

⁵ Only included if time of assessment collected on form. Percentage was calculated based on the number of participants who received XR-NTX injection.

[figure not shown]

Figure 20: Average Daily Maximum COWS Score in Rapid Procedure by Phase

Example figure provided.

[figure not shown]

Figure 21: Average Daily COWS Score in Rapid Procedure by Phase

Example figure provided.

[figure not shown]

Figure 22: Average Daily SOWS Score in Rapid Procedure by Phase

Example figure provided

[figure not shown]

Figure 23: Average VAS Craving Score at Time of Assessment in Rapid Procedure by Phase

Example figure provided.

[figure not shown]

Figure 24: Average Maximum VAS Craving Score within 24 Hours in Rapid Procedure by Phase

Example figure provided.

Table 47: Covariate Adjusted Modeling Results for Opioid Withdrawal as Measured by COWS and SOWS During the Induction Phase

Effects	COWS Daily Maximum				COWS Daily Average				SOWS			
	Odds ¹ Ratio	95% Lower Confidence Limit	95% Upper Confidence Limit	p-value	Odds ² Ratio	95% Lower Confidence Limit	95% Upper Confidence Limit	p-value	Estimate	95% Lower Confidence Limit	95% Upper Confidence Limit	p-value
Rapid versus Standard	X.xx	X.xx	X.xx	0.xxx								
Inpatient day												
Nexus Recovery Center versus ADAPT												
Avery Road Treatment Center versus ADAPT												
Aspire Health Partners vs. ADAPT												
Gibson Recovery Center versus ADAPT												
Stony Brook Eastern Long Island Hospital versus ADAPT												

¹The odds of at least one moderate to severe daily COWS score (maximum score ≥ 12).

²The odds of presence of moderate to severe average daily COWS score (average score ≥ 12).

Table 48: Covariate Adjusted Modeling Results for Craving for Opioids During the Induction Phase								
Effects	Craving VAS at Time of Assessment				Maximum Craving VAS within 24 Hours			
	Estimate	95% Lower Confidence Limit	95% Upper Confidence Limit	p-value	Estimate	95% Lower Confidence Limit	95% Upper Confidence Limit	p-value
Rapid versus Standard	X.xx	X.xx	X.xx	0.xxx				
Inpatient day								
Nexus Recovery Center versus ADAPT								
Avery Road Treatment Center versus ADAPT								
Aspire Health Partners vs. ADAPT								

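### SAP 8.5, binary COWS code: AR(1) on a single random intercept has no effect, so serial correlation between days is not modelled and the inpatient-day interval in Table 47 may be too narrow

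*SAP*

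**What the plan says.** The prose of SAP 8.5 defines two binary daily outcomes, maximum COWS of at least 12 and average COWS of at least 12, and says they "will be analyzed using a mixed-effects model with logit-link function". It names no correlation structure over days.

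The code is introduced as "SAS code example that may be used to analyze binary COWS outcome". It calls "proc glimmix data = secondout method = quad IC=PQ", with the mean model "model outcome (event='1')= trt site day step/ dist = binary link = logit solution oddsratio" and the random-effects line "random intercept / subject=patid type=ar(1". The CLASS statement lists participant, site, procedure and step, but no categorical day.

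For the continuous SOWS and VAS scores, the next code block has a participant random intercept and a separate line, "repeated day_cat/ type = AR(1) subject = patid", with a categorical day variable defined for that purpose. In SAP 8.2, the alternative model for the primary outcome puts AR(1) on step within site.

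The results go to Table 47, "Covariate Adjusted Modeling Results for Opioid Withdrawal as Measured by COWS and SOWS During the Induction Phase". It sets COWS maximum, COWS average and SOWS side by side. Its rows are Rapid versus Standard, inpatient day and the site contrasts, each with 95% limits and a p-value. SAP 11.0 adds: "The secondary outcomes will use a two-sided test with 5% type I error rate".

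**The concern.** An AR(1) structure needs at least two random effects per subject to correlate. In the SOWS/VAS code these are the days, and in the SAP 8.2 alternative model they are the steps. In the binary COWS code there is only the intercept, so the option is silently ignored. An analyst who copies the block could believe that serial correlation has been fitted, and a reader of Table 47 would assume that its three column groups were handled alike.

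Withdrawal scores on adjacent days could well be more alike than scores a week apart. If so, a model that treats the days as exchangeable given the intercept overstates how much information the daily series carries about a trend over days. The printed limits and p-value for inpatient day would then look more precise than they are, for both COWS outcomes.

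**Working it through.** **Structure.** Write the random part of the linear predictor for participant i on day t as b_i, with Var(b_i) = σ². For any two days s and t, Cov(b_i, b_i) = σ², whatever |t − s|. The matrix passed to the AR(1) option is 1x1, with entry σ²·ρ^0 = σ². The parameter ρ does not enter the likelihood. A day-level AR(1) would instead contribute τ²·ρ^|t−s|.

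**No figure to reproduce.** Table 47 is a blank shell. The documents give no autocorrelation, no participant variance and no rate of COWS of 12 or more. The size therefore has to be simulated over a range.

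**Inputs from the SAP.** The layout is 6 sites x 5 steps x 15 = 450 participants (12.0). Induction lasts about 6 days in RP and 13 in SP (12.0), with injection possible to Day 7 and Day 14 (Tables 3 and 4). Success is 0.70 and 0.55 (12.0). The daily series was simulated up to 7 and 14 days, with early stopping at those success rates.

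**Assumed inputs.** Participant intercept SD, latent daily AR(1) SD and autocorrelation as in the table; day slope −0.15; procedure log odds ratio 0.3.

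**Method.** The SAP's working model (random-intercept logit; fixed procedure, site, linear day and step; 21-point quadrature) was fitted to 22 datasets per scenario. Its model-based SE was divided by the participant-clustered sandwich SE. A ratio of 1 means the printed interval has the right width; 0.80 means it is 20% too narrow.

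| Participant SD | Daily SD | Autocorrelation | Days with COWS ≥12 | Ratio, day | Ratio, RP vs SP |
|---|---|---|---|---|---|
| 1.5 | 0 | none (control) | 25% | 1.005 | 0.995 |
| 1 | 1 | 0.5 | 25% | 0.924 | 1.004 |
| 1 | 1 | 0.8 | 24% | 0.891 | 1.002 |
| 1 | 1.5 | 0.5 | 27% | 0.885 | 0.999 |
| 1 | 1.5 | 0.8 | 27% | 0.813 | 1.000 |
| 0 | 2 | 0.5 | 28% | 0.854 | 0.979 |
| 0 | 2 | 0.7 | 28% | 0.779 | 0.994 |
| 0 | 2 | 0.8 | 28% | 0.748 | 0.993 |
| 0 | 2 | 0.9 | 28% | 0.752 | 0.999 |
| 0 | 3 | 0.8 | 33% | 0.668 | 0.990 |
| 0 | 2 | 0.8 | 13% | 0.792 | 0.987 |

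The narrowing of the day interval runs from 1 − 0.924 = 8% to 1 − 0.668 = 33%. The control shows that it comes from the missing serial structure. Taking the robust SE as correct, a nominal 95% day interval covers 2Φ(1.96 x ratio) − 1: about 93% at 0.92, 89% at 0.81 and 81% at 0.67.

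**Check against the empirical SD** (300 datasets each):
- Participant SD 0, daily SD 2, autocorrelation 0.8: day 0.0128/0.0165 = 0.78; RP 0.242/0.247 = 0.98.
- 1, 1.5, 0.8: day 0.0134/0.0156 = 0.86; RP 0.266/0.282 = 0.94.
- 0, 3, 0.8: day 0.0125/0.0178 = 0.70; RP 0.280/0.286 = 0.98.

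The Monte Carlo error of these ratios is about 1/√(2 x 299) = 4%.

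**Separate runs** (420 participants, 220 datasets per scenario, autocorrelation 0.7, no procedure effect). The ratio of empirical SD to model SE for day was 1.22 (participant SD 1, daily SD 1.5) and 1.26 (0, 2), so the SE is 1 − 1/1.22 = 18% and 1 − 1/1.26 = 21% too small. For RP the ratio was 1.05 in both, with rejection rates of 5.5% and 6.4%.

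**Why the two rows differ.** RP versus SP compares different participants within the site and step terms, and the estimated intercept variance absorbs most of the extra between-participant variation. The day slope is estimated within participants, where slow drift mimics a trend that the model takes to be independent noise.

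**The case against.** The strongest defence has four parts.

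- **The prose is satisfied.** It promises a logit mixed model, and a random-intercept logit is one. The code is offered only as an example. This stands: that serial correlation was intended is inferred from the AR(1) option itself and from the neighbouring code, and no sentence in the SAP commits to it for COWS. It is still the only code given for this outcome, and one of its options does nothing.
- **Inpatient day is an adjustment term.** The hypotheses in SAP Table 5 concern Rapid against Standard, and SAP 11.0 describes the key secondary outcomes as not confirmatory. This also stands and keeps the point minor. Table 47 nevertheless prints limits and a p-value for day.
- **Correlation between days is not ignored.** A reader might infer that the model treats a participant's days as independent. It does not: the intercept gives equal correlation at every lag, and only the lag-decaying part is missing.
- **The comparison of interest is not shown to be harmed.** A reader might infer from the 5.5% and 6.4% rejection rates that the Rapid-versus-Standard test is anti-conservative. With 220 datasets the Monte Carlo SE of a 5% rate is √(0.05 x 0.95/220) = 1.5 points, so both lie within one SE of nominal. The ratio of 1.05 has an error of about 1/√(2 x 219) = 0.05. Against the robust SE the shortfall is about 0% to 2%.

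**Conclusion.** The point holds as a coding fault with limited reach. The AR(1) option is inert; this follows from the code alone and needs no assumption.

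Its consequence is conditional. If daily COWS is serially correlated beyond a constant participant effect, the inpatient-day limits for both COWS outcomes are too narrow and the p-values too small. The range found depends on the assumed variances and autocorrelation, so a single figure such as 20% should not be read as a property of this trial. With no serial correlation there is no error. The documents do not support a claim that the Rapid-versus-Standard conclusion is at risk. No planned hypothesis depends on the day row, so this is a desirable correction and not an essential one.

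**What to change.** **Preferred.** Remove `type=ar(1)` from the COWS code, keep `random intercept / subject=patid`, and request sandwich standard errors clustered on participant for both COWS models. State in SAP 8.5 that the model assumes exchangeable days and that the robust errors guard against serial correlation. The cost is slightly wider intervals, mainly for day. The odds ratios and the quadrature fit do not change.

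**Alternative.** Keep the participant intercept, add `day_cat` to CLASS, and specify a residual-side AR(1) over `day_cat` within participant. This parallels the SOWS/VAS code. Quadrature does not accept a residual-side structure, so the fit must move to pseudo-likelihood. The cost is a change of estimation method for a secondary model.

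Replacing the intercept with a random effect for each day is not recommended. It would drop the participant intercept and make the procedure odds ratio conditional on daily effects, a different quantity from the one now planned. Quadrature over that many effects is also impractical.

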The research recruitment phase begins with informed consent up to one week before or up until the fourth day of inpatient admission to the study site. During the inpatient admission intake/evaluation or the first four days of an inpatient admission, clinical staff, as part of standard clinical procedures, will conduct a medical and psychiatric workup, and conduct a shared – decision-making process regarding choice of maintenance medication to be initiated during the inpatient stay. During this process research staff will provide information about the study to potential participants, describing XR-NTX as an option for relapse-prevention to opioid dependence following detoxification, and the study plan to monitor the progress of patients undergoing initiation and initial months of treatment with XR-NTX using materials prepared for the study. For scheduled admissions, this information may be provided in advance of the admission. Once a patient decides (with their clinicians) to pursue XR-NTX treatment, then the patient can be offered informed consent to participate in the study.

After the participant provides written informed consent, the participant will be evaluated for study eligibility. Eligible participants will continue with study assessments. Participants may be stabilized

on buprenorphine before study enrollment but those who received methadone at treatment outset (e.g., in the ER or upon arriving at the unit) are not eligible for enrollment.

Clinical Induction Procedures

Following the initial buprenorphine treatment, the units will provide participants with treatment guided by the regimen for the respective study arm as implemented by clinical staff at the detoxification program (Tables 6A and 6B).

Standard Procedures: The plan is for 13-14 days from first dose of buprenorphine in the Standard Procedures (SP) for induction, detailed in Table 6A; this includes a 5-day buprenorphine taper followed by an 8-day washout before being eligible for the XR-NTX injection (as determined by the naloxone challenge, naltrexone titration, or toxicology). In case that participant does not meet criteria of eligibility by Day 14, the eligibility determination can be repeated on subsequent days. Since the SP regimen will be the standard of care for XR-NTX initiation during the SP phase of the participation of a Site, there will be flexibility based on clinical judgment.

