Rapid Procedures: The plan is for 5-7 days from first dose of buprenorphine in the Rapid Procedures (RP) for induction, detailed in Table 6B; this includes 1 day of buprenorphine followed by 1-day washout and a 4-day period of treatment with low-doses of oral naltrexone. Adjunctive medication will be given throughout the RP. Again, since the RP regimen will be the standard of care for XR-NTX initiation during the RP phase of the participation of a Site, there will be flexibility based on clinical judgment. For example, it is possible that some participants will not be able to tolerate naltrexone 6 mg on Day 6 and in those participants, XR-NTX may be administered on Day 7 or thereafter.

After administration of XR-NTX participants will continue treatment per standard clinical practice. The day after the first XR-NTX injection is received or the day after the decision to discontinue XR-NTX induction is considered the Post-Induction Day 1. Participants who receive the first XR-NTX injection will be classified as meeting criteria for “XR-NTX induction success.” Participants who discontinue the induction phase before receiving the XR-NTX injection will be classified as “XR-NTX induction failure.” These participants will continue in the study but will only follow up at Week 4 and Week 8.

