12.0 SAMPLE SIZE AND POWER

The CTN-0097 study design is represented schematically as the Design Pattern matrix of Figure 1. The design pattern matrix gives table a schematic representation of the optimized stepped-wedge design compared with a standard stepped-wedge design alternative. Rows are sites, columns are blocks of time (steps), and cells contain 0 for SP or 1 for RP. The optimized stepped-wedge design provides more power to detect a treatment effect than a similar standard stepped-wedge design (Thompson *et al.*, 2017). The primary outcome measure is the proportion of patients who receive the first XR-NTX injection at the end of the induction phase, which is approximately Day 6 in the RP and Day 13 in the SP (binary: did or did not receive first injection of XR-

NTX).

Figure 1: Design Pattern Matrix

Optimized Stepped-Wedge Design						Standard Stepped-Wedge Design						
		Time Block							Time Block			
		1	2	3	4	5			1	2	3	4
Site	1	1	1	1	1	1			1	0	1	1
	2	0	1	1	1	1			2	0	1	1
	3	0	0	1	1	1			3	0	0	1
	4	0	0	0	1	1			4	0	0	1
	5	0	0	0	0	1			5	0	0	0
	6	0	0	0	0	0			6	0	0	0

Values of Parameters Underlying Power Simulations

Probability of Success in the SP arm: The assumed success probability in the SP initiation regimen is based on the mean success rate in the XR-NTX arm of CTN-0051 (Lee *et al.*, 2018), which is 55% for sites 02011, 02017, and 02052 pooled together. These are sites that are similar to the types of sites that would be eligible for this study.

Probability of Success in the RP arm: A difference in the proportion of successes of 15% with an overall success of 55% in the SP arm (as in study CTN-0051) and 70% in the RP are assumed. Estimates are based on the results of a prior controlled study, which compared Standard and Rapid XR-NTX procedures and found a 23.4% difference (56.1% vs. 32.7%) (Sullivan *et al.*, 2017). A slightly smaller true treatment difference (15%) is assumed, due to the more structured, inpatient/short-term residential setting of sites in the current study

Margin of non-inferiority: To show non-inferiority of RP to SP, a 10% margin of non-inferiority is assumed, which corresponds to an odds ratio of 0.67 (proportion of success in RP = 0.45, proportion of successes in SP = 0.55). To show RP is non-inferior to SP, the lower bound of the two-sided 95% CI for the odds ratio for RP vs SP needs to be higher than 0.67.

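### The craving and withdrawal models adjust for day with one straight line shared by both arms although RP and SP are observed over different spans of days, so a curved course would leak into the RP coefficient

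*SAP*

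**What the plan says.** SAP 8.5 plans mixed models for the daily induction scores, "adjusting for induction procedure, site, step, and days since admission". The example program for continuous SOWS and VAS has "model outcome = trt site day step/ solution cl". The variable list below it defines day as continuous. A second version exists only for the covariance structure: "day_cat- days since admission to the unit (categorical) as required by the repeated statement in the model", used in "repeated day_cat/ type = AR(1) subject = patid". There is no quadratic or spline term and no treatment-by-day term. The binary COWS program in the same section also has day in MODEL but not in CLASS, so it too gets one slope.

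The text says the continuous-score models may be used, but that the binary COWS outcomes will be analysed with a logit mixed model. SAP 18.0 lists adjusted COWS, SOWS and craving results among the outputs to be provided. Shell Tables 47 and 48 (SAP 19.1.8) show one inpatient-day row beside the Rapid versus Standard row, which fits a single slope.

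On observation time, SAP 12.0 puts the end of induction at "approximately Day 6 in the RP and Day 13 in the SP". Protocol 6.1.4 describes RP as "this includes 1 day of buprenorphine followed by 1-day washout and a 4-day period of treatment with low-doses of oral naltrexone" and SP as "this includes a 5-day buprenorphine taper followed by an 8-day washout". SAP 3.2.1 counts days from admission and allows up to 30.

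**The concern.** Participants contribute daily scores only until induction ends, and that point differs by arm by design. Early days hold both arms and late days hold mostly SP. One line fitted to all of it takes its slope largely from SP's long series. If the true course bends, early days lie off that line, and because RP is observed almost only on early days, its coefficient picks up the misfit.

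Curvature is plausible. Protocol 4.1.2 speaks of the most severe symptoms falling in the first several days, and treatment changes by day in both regimens. The stated hypothesis (SAP Table 5) is comparable withdrawal and craving, while Protocol Appendix B warns that withdrawal may be more severe under RP. A coefficient pushed one way could suggest a tolerability problem that does not exist; pushed the other way it could hide one that does.

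**Working it through.** **Day counts.** RP: 1 + 1 + 4 = 6. SP: 5 + 8 = 13. Both agree with SAP 12.0. The documents give no SD, curve or power for these outcomes, so everything below except the design and success rates is assumed.

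**Mechanism by hand.** Give both arms the same course f(d), so the true RP effect is 0. Let RP be observed on Days 1-6 and SP on Days 1-13, with 225 participants per arm. With independent residuals and a random participant intercept, the expected RP coefficient is

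bias = (mean f in RP - mean f in SP) - b x (mean day in RP - mean day in SP),

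where b is the pooled within-person slope.

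- Mean days: (1+6)/2 = 3.5 and (1+13)/2 = 7, difference -3.5.
- Assume SOWS f(d) = 25 exp(-(d-1)/2), a fast decline. Sums of f: 60.37 over 6 days and 63.44 over 13 days. Means: 10.06 and 4.88, difference 5.18.
- Slope: the within-person cross-products are -76.8 and -284.1; the sums of squares of day are 17.5 and 182. So b = -360.9/199.5 = -1.81.
- Bias = 5.18 - (-1.81)(-3.5) = 5.18 - 6.33 = -1.15 points.

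If f is a straight line, the two terms cancel and the bias is 0.

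**Exact expected estimates under the SAP model** (6 sites x 5 steps x 15 participants; fixed arm, site, step and linear day; random intercept plus AR(1); 6 versus 13 days; between-person SD 5-8, within-person SD 7-8, AR(1) correlation 0-0.5):

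- straight-line course: 0.00
- exponential decline, time constant 4 days: -0.53 to -1.24
- exponential decline, time constant 2 days: -1.15 to -2.28 (the hand value is the case of correlation 0)
- decline then plateau: -0.66 to -1.69
- peak on Day 3: +1.22 to +1.38
- late hump: -0.55 to -0.01

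With categorical day the bias was 0.00 in every one of these shared-course cases, at almost no cost (SE 1.06 against 1.05, or 1.51 against 1.50).

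**Simulation with REML-estimated covariance** (SDs 5 and 8, correlation 0.3, 100 runs each). Cells show mean RP effect and rejection at nominal 5%. Early leavers use the SAP success rates of 0.55 and 0.70.

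| Course | Lengths | Linear day | Categorical day |
|---|---|---|---|
| Decline, 4 days | 6 v 13 | -0.91, 8% | +0.05, 3% |
| Decline, 2 days | 6 v 13 | -2.14, 37% | +0.06, 6% |
| Peak Day 3 | 6 v 13 | +1.31, 19% | +0.03, 3% |
| Decline, 4 days | early leavers | -0.77, 6% | +0.13, 4% |
| Decline, 2 days | early leavers | -2.02, 35% | -0.08, 1% |
| Peak Day 3 | early leavers | +0.53, 7% | +0.03, 4% |

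Monte Carlo error on a true 5% rate is sqrt(0.05 x 0.95/100) = 2.2 percentage points. Rough check of the 37%: mean SE 1.33, so 2.14/1.33 = 1.61 and Phi(1.61 - 1.96) = Phi(-0.35) = 36%.

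**Varying the lengths.** For a Day 3 peak with SDs 8 and 8 and early leavers, bias was +0.7 to +1.2 with 7-12% rejection. Letting RP run 6-11 days and SP 12-19 cut it to -0.1 to +0.5 with 5-6.5%. Across further assumed curves with early leavers, overlapping lengths and AR(1), the range was about -1.9 to +1.9 points and 5-25%.

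**When the arms do not share a course.**

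- RP 4 points higher from Day 3 on (true mean over Days 1-6: 4 x 4/6 = 2.67): linear day gave 2.06, categorical day 2.70.
- SP 6 points higher on Days 6-10 only, with no difference on Days 1-5: linear day gave -2.40 and categorical day still gave -1.58. A single arm coefficient averages unlike days whatever form day takes.

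**The case against.** The strongest reply is that the size is unknown. The day counts are planned lengths from the first buprenorphine dose, whereas the model counts from admission. The SAP expects pre-buprenorphine days in RP, clinicians may modify both regimens, and induction may last 30 days. More overlap weakens the link between arm and day, and for an early peak the bias then nearly vanishes. This stands: no single figure is the expected effect. A reader might take the early-peak case at near-fixed lengths, with a known random-intercept covariance (+1.6 to +1.8 points, 18-23% false positives), as the likely result. The documents do not support that; other plausible curves reverse the sign.

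A reader might also infer that moving day_cat into MODEL settles the matter. It does so only if both arms share one course by day. RP starts oral naltrexone on Day 3 while SP tapers to Day 5 and then washes out (Protocol Tables 6A and 6B), so a shared course is doubtful, and the last example above shows what remains.

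Third, scores are also tabulated and plotted by day and by procedure phase (SAP Tables 43-46), the continuous-score code is an example, and SAP 11.0 calls key secondary outcomes not confirmatory. That limits the consequence. It does not remove the bias from the adjusted estimate and p-value in Tables 47 and 48, and for binary COWS the model is stated as planned.

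**Conclusion.** The point holds as a model-form weakness in a key secondary comparison. One linear day term, with observation spans that differ by arm, lets any curved course enter the RP coefficient. Under the assumed curves and SDs with no true effect, the bias was about -2.3 to +1.9 SOWS points on a 0-64 scale and the rejection rate about 5% to 37%. These ranges describe the settings tried and are not bounds: the same bias with smaller SDs would reject more often. For mild curvature the bias is under about 1 point and the error rate hardly moves. The simulations were for SOWS; the argument carries to craving and to binary COWS through the same day term, but no size was computed for them. Nothing here bears on the primary non-inferiority analysis, which has no day term.

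**What to change.** - **SOWS and VAS:** replace day with day_cat in MODEL, add a treatment-by-day_cat term, and define the RP-SP contrast as the average of the day-specific differences over a pre-specified window when both arms are under observation (Days 1-6, for example).
- **Binary COWS:** add day to CLASS within that window, or use a low-order spline. A full set of up to 30 day levels would be sparse late on and could fail to converge.
- **Reporting:** change Tables 47 and 48 to show the windowed contrast and the day-specific differences in place of the single inpatient-day row, and state the window in SAP 8.5.

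No new data are needed. SP-only days no longer inform the contrast, so SP's later washout is described only in the by-day and by-phase tables. The window also sets the question: in the SP-rise example, Days 1-5 would give 0 and Days 1-6 would give -6/6 = -1.0. The loss of precision is small: SE about 1.55 against 1.51 under the assumed SDs, or 1.55/1.51 = 1.03.
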